### 9.2 Responsibility for Analyses

The statistical analysis of the data obtained from this study will be conducted by, or under the direct auspices of, the Early Clinical Development Statistics Department in collaboration with the Quantitative Pharmacology and Pharmacometrics Department and Translational Pharmacology Department of the Sponsor.

If, after the study has begun, changes are made to the statistical analysis plan stated below, then these deviations to the plan will be listed, along with an explanation as to why they occurred, in the CSR.

### 9.3 Hypotheses/Estimation

#### Primary Estimation:

MK-3402 AUC0-inf following a single IV dose of MK-3402 administered to participants with varying degrees of RI (mild, moderate, severe, ESRD before HD, ESRD after HD) will be estimated and compared to MK-3402 AUC0-inf when administered to healthy matched control participants.

#### Secondary Estimation:

The extent to which MK-3402 is removed by hemodialysis from the plasma (plasma MK-3402 CLD,plasma or the dialysate CD, AED, AED (%dose), and CLD,dialysis) will be estimated.

MK-3402 Ae0-24, Fe, and CLr following a single IV dose of MK-3402 administered to participants with varying degrees of RI, as appropriate, will be estimated and compared to those estimated in healthy matched control participants.

### 9.4 Analysis Endpoints

The primary PK endpoints are plasma MK-3402 AUC0-inf, Ce0, Tmax, elimination terminal t1/2, CL, and Vd following a single MK-3402 IV dose in participants with mild, moderate, severe renal impairment, ESRD or in healthy matched control participants.

The secondary PK endpoints are plasma MK-3402 CLD,plasma or the dialysate CD, AED, AED (%dose), and CLD,dialysis and urine MK-3402 Ae0-24, Fe, and CLr following a single MK-3402 IV dose in participants with mild, moderate, severe impairments, ESRD or in healthy matched control participants.

The secondary safety endpoints are AEs, VS, 12-lead ECGs, and laboratory safety tests.

The exploratory endpoint is eGFR at baseline.

### 9.5 Analysis Populations

The following populations are defined for the analysis and reporting of data. All participants will be reported, and their data analyzed, according to the treatment(s) they actually received.

*All Participants as Treated (APaT):* The All Participants as Treated Population consists of all participants who received at least one dose of treatment. This population will be used for assessments of safety and tolerability.

*Per-Protocol (PP):* The Per-Protocol Population consists of the subset of participants who comply with the protocol sufficiently to ensure that generated data will be likely to exhibit the effects of treatment, according to the underlying scientific model. Compliance covers such considerations as exposure to treatment, availability of measurements and absence of important protocol deviations. Important protocol deviations will be identified to the extent possible prior to unblinding by individuals responsible for data collection/compliance, and its

analysis and interpretation. Any participants or data values excluded from analysis will be identified, along with their reason for exclusion, in the CSR. At the end of the study, all participants who are compliant with the study procedure as aforementioned and have available data considered sufficient to exhibit the effect of treatment will be included in the Per-Protocol dataset. This population will be used for the PK analyses.

## 9.6 Statistical Methods

### Pharmacokinetics:

#### **Primary Analysis**

If a different group of healthy matched control participants is needed to match the mean age and BMI for the RI and ESRD groups, then separate analyses will be performed for the populations as follows:

- Mild RI and moderate RI versus an appropriate group of healthy matched control participants;
- Severe RI versus an appropriate group of healthy matched control participants;
- ESRD participants (non-HD and HD) versus an appropriate group of healthy matched control participants.

If a single set of healthy matched control participants can be used for comparison with all RI and ESRD groups, the following analysis pooled over all populations will be used.

Separately for each pharmacokinetic parameter, individual values of plasma MK-3402 AUC0-inf and Ce0i will be natural log-transformed and evaluated with a linear fixed-effects model containing a categorical effect for populations. The REPEATED statement with the GROUP=Population option will be used in SAS PROC MIXED to estimate separate variances for each population. The Kenward and Roger adjustment will be used to calculate the denominator degrees of freedom for the fixed-effect (DDFM=KR).

Ninety-five percent (95%) CIs for the least squares means for each population will be constructed on the natural log scale and will reference the t-distribution. Exponentiating the least-squares means and their corresponding 95% CIs will yield estimates for the population GMs and CIs about the GMs on the original scale.

To compare participants with RI in each of the renal categories (mild RI, moderate RI, severe RI, ESRD non-HD and ESRD HD) to matching participants with normal renal function, a 2-sided 90% CI for the true difference in means (RI - normal renal function) will be calculated for each PK parameters (AUC0-inf and Ce0i) using the mean square error from the model and referencing a t-distribution. For each of the RI populations, these confidence limits will be exponentiated to obtain the 90% CI for the true GMRs (RI/normal renal function) for each PK parameter.

Figures showing individual PK values with GMs (95% CIs) by population, plotted on the natural log scale, will be provided for AUC0-inf and Ceoi.

## Secondary Analysis

To evaluate the extent to which MK-3402 is removed from plasma by HD, a linear mixed effect model with population (ESRD non-HD, ESRD HD) as a fixed effect will be used. An unstructured covariance matrix will be used to allow for unequal treatment variances and to model the correlation between the 2 treatment measurements within each participant via the REPEATED statement in SAS PROC MIXED. Kenward and Roger's method will be used to calculate the denominator degrees of freedom for the fixed effects (DDFM=KR).

A natural log transformation will be applied to AUC0-inf and Ceoi. For each PK parameter, 95% confidence intervals for the least squares means will be constructed on the natural log scale and will reference the t-distribution. Exponentiating the least-squares means and their corresponding 95% CIs will yield estimates for the population GMs and CIs about the GMs on the original scale.

A 2-sided 90% CI for the true difference in means (ESRD HD – ESRD non-HD) will be calculated for each pharmacokinetic parameter (AUC0-inf and Ceoi) using the mean square error from the model and referencing a t-distribution. These confidence limits will be exponentiated to obtain the 90% confidence interval for the true ratio (GMR) of geometric means (ESRD HD / ESRD non-HD) for each PK parameter.

Plots with individual ratios overlaid with GMR and corresponding 90% CI will be provided for AUC0-inf and Ceoi.

Separately for each urine PK parameter, where possible, individual values of Ae0-24, Fe and CLr will be natural log-transformed and evaluated with a linear fixed-effects model, which is described in the primary analysis. Ninety-five percent (95%) CIs intervals for the least squares means for each population will be constructed. To compare participants with RI in each of the renal categories (mild RI, moderate RI, severe RI, ESRD non-HD and ESRD HD) to matching participants with normal renal function, a 2-sided 90% CI for the true ratio of means (RI/normal renal function) will be calculated for each urine PK parameter (Ae0-24, Fe and CLr).

## Exploratory Regression Analysis

In addition to running the primary regression analysis below using BSA normalized eGFR as the measure of renal function for each participant, the analysis will also be run using BSA un-normalized eGFR and CrCL from CG equation.

Separately for each PK parameter, individual values of plasma MK-3402 AUC0-inf and Ceoi will be evaluated with a linear fixed effects model containing eGFR as a continuous variable. The participant's mean renal function value derived from 2 serum creatinine measurements at Screening will be used for the analysis. Estimates of the slope and intercept, together with corresponding ninety five percent (95%) CIs will be obtained. The estimated mean and

corresponding 95% CI for each renal impairment group will be predicted at the midpoint of the defined eGFR range for each group (60, 45, and 22.5 for mild, moderate, and severe, respectively). However, for the normal renal function group, the estimated mean and corresponding 95% CI will be predicted at the median of the observed eGFR values. Sample SAS code is given below.

```
Proc mixed data=pk ;  
  
model AUC= eGFR / s cl DDFM=KR alpha=0.05 outpm=normres;  
estimate "predicted AUC in severe" int 1 eGFR 22.5/alpha=0.1 cl e;  
  
estimate "predicted AUC in moderate" int 1 eGFR 45/alpha=0.1 cl e;  
  
estimate "predicted AUC in mild" int 1 eGFR 60/alpha=0.1 cl e;  
  
estimate "predicted AUC in normal" int 1 eGFR xx /alpha=0.1 cl e;  
  
*xx is median eGFR for normal renal function group***;run;
```

The data will be examined for departures from the assumptions of the model. The residuals from the model will be examined for normality using diagnostic plots such as residuals vs predicted values and normal probability plots of residuals. Lack of fit will also be visually assessed.

If the model used does not fit the data adequately, other models, such as natural log-transformed PK vs renal function or natural log-transformed PK vs natural log-transformed renal function, will be explored. Other transformations or nonlinear models will also be considered.

Additionally, plots of MK-3402 PK parameter values (AUC0-inf, Ceoi) versus eGFR along with a regression line and 95% confidence bands for regression line will be constructed. Different symbols will be used to identify different renal function groups. Separate plots of AUC0-inf and Ceoi values vs age and body weight will be provided.

Summary Statistics using BSA un-normalized eGFR: The participants will be recategorized into different renal categories based on their BSA un-normalized eGFR and nonmodel based summary statistics by population will be provided for (plasma AUC0-inf, Ceoi, Tmax, elimination terminal t1/2, CL, and Vd, and urine Ae0-24, Fe, and CLr, as applicable).

Analysis using CrCl (CG equation): The participants will be recategorized into different renal categories based on their CrCl obtained from CG equation and nonmodel based summary statistics by population will be provided for (plasma AUC0-inf, Ceoi, Tmax, elimination terminal t1/2, CL, and Vd, and urine Ae0-24, Fe, and CLr, as applicable).

Individual values will be listed for each PK parameter (plasma MK-3402 AUC0-inf, Ceoi, Tmax, elimination terminal t1/2, CL, and Vd, plasma MK-3402 CLD,plasma or the dialysate CD, AED, AED (%dose), and CLD,dialysis, and urine MK-3402 Ae0-24, Fe, and CLr) by population, and the following (nonmodel-based) descriptive statistics will be provided: N

(number of subjects with nonmissing data), arithmetic mean, standard deviation, arithmetic percent CV (calculated as 100 x standard deviation/ arithmetic mean), median, minimum, maximum, geometric mean, and geometric percent CV (calculated as 100 x sqrt( exp(s) - 1), where s is the observed variance on the natural log-scale).

**Safety:** The safety and tolerability of MK-3402 will be monitored by clinical assessment of adverse experiences and other safety measurements (eg, labs, VS, ECGs).

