## 4.2 Scientific Rationale for Study Design

MK-3402 is likely to be used in patients with various degrees of RI, as a proportion of patients with serious gram-negative infections have baseline RI, and also patients can develop acute renal failure in the setting of gram-negative sepsis. The primary purpose of this trial is to understand the effect of RI on the pharmacokinetics of MK-3402 in order to guide dosing recommendations in these patients.

CLR is expected to be the major elimination pathway for MK-3402. Parameter estimates were obtained from an interim PK analysis, indicating that ~ 60% of MK-3402 is excreted in the urine following a single IV dose. The potential effect of RI on single-dose PK will be a reduction in clearance, thereby increasing the terminal t1/2 and AUC. A change in the Cmax following a single dose is not anticipated. However, these predictions do not take into consideration of the potential contribution from non-renal elimination (e.g. hepatic elimination), which might involve in the elimination of MK-3402. It is noted that the potential for RI to affect the non-renal clearance of compounds like MK-3402 cannot be ruled out.

Due to the projected impact of RI on MK-3402 PK, a PK study design was selected that will enable the estimation of effect across the spectrum of RI, in order to inform dose adjustments which may be needed in each of mild, moderate, and severe RI, as well as the establishment of recommendations for dosing with respect to HD.

Plasma protein binding is often altered in patients with impaired renal function and is assessed in some instances in renal insufficiency trials. However, this study will not assess plasma protein binding due to the low to moderate protein binding seen in vitro and that binding is not concentration dependent in the clinically relevant concentration range.

MK-3402 will be administered in a fasted state. It is recognized that food will likely have minimal impact on the PK of an IV administered drug. However, food may have systemic effects, in particular on drug metabolizing enzymes. As such, study drug will be administered in the fasted state in order to reduce variability.

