MK-3402 was observed to be eliminated predominantly through renal elimination (~ 60%) and participants with renal insufficiency are projected to attain higher exposures relative to participants with normal renal function due to decreased CLr. It is assumed that there is generally a linear relationship between eGFR and CLr which will impact the terminal t1/2 and AUC, as shown in the table below. Projections have been based on the preliminary PK analysis of the single ascending dose study. Of note, it is difficult to provide accurate estimates for ESRD, due to the severity of the illness. One assumption made when estimating the parameter values is that Vd does not change with decease of renal function. Clinical safety data are available up to 600 mg delivered as a single dose and 1100 mg delivered as a divided dose which have been generally well tolerated with AUC0-inf of 655  $\mu\text{M}\cdot\text{hr}$  at the 1100-mg dose. These doses are projected to provide a greater than 6.7x exposure margin for the 100-mg proposed dose in ESRD (not on dialysis) patients and a 12.9x exposure margin in healthy participants.

Regarding the 1-month MK-3402/REL combination toxicity study (as discussed above), at the NOEL dose (20 mg/kg/day MK-3402 + 50 mg/kg/day REL), the exposures and safety margins to 100 mg dose of MK-3402 to be administered in the current study (P004; projected for ESRD participants not on dialysis) are AUC0-24hr= 253  $\mu\text{M}\cdot\text{hr}$  (2.6X) and Cmax= 76  $\mu\text{M}$  (5.1X) [Table 7].

Table 7 MK-3402 Systemic Exposure Multiples Between Monkeys in the 1-Month Combination Toxicity Study with REL (TT#20-1000) and Projected Human Exposure at 100 mg in P004

1-month IV Combination Tox Study in Monkeys	AUC $\mu\text{M} \cdot \text{hr}$	Exposure Multiple a	C max $\mu\text{M}$	Exposure Multiple a
Control				
MK-3402 Placebo	0	0		
Low Dose (LD)				
MK-3402 20 mg/kg/day	253	2.6X	76	5.1X
High Dose (HD)				
MK-3402 50 mg/kg/day	633	6.5X	184	12.4X

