a. Exposure margins are calculated to the projected exposure at the maximum protocol-specified dose of MK-3402 (100 mg, 30 min IV infusion, AUC 0-inf of 98 $\mu\text{M} \cdot \text{hr}$ , C max 14.8 $\mu\text{M}$ ) in ESRD participants not on dialysis. Plasma protein binding is similar between species, with similar % unbound for MK-3402 (78% in monkeys and 68% in humans).				

No treatment-related ECG-findings have been observed in nonclinical studies in rhesus monkeys at significantly higher doses for MK-3402 alone (exposures in monkeys up to 550 mg/kg/day: AUC0-24hr = 7210  $\mu\text{M} \cdot \text{hr}$ , 74X and Cmax = 1940  $\mu\text{M}$ , 131X relative to the projected exposure at 100 mg).

Single dose PK are anticipated to be predictive of multiple dose PK; accumulation is expected to be modest, with an accumulation ratio of ~ 1.3 in healthy participants. As this is a Phase 1 assessment of MK-3402 in humans, and the PK, pharmacodynamic and safety profiles of the compound are still being evaluated, modifications to the dose or dosing regimen may be required to achieve the scientific goals of the study objectives and/or to ensure appropriate safety monitoring of the study participants. Details of allowed modifications are provided in Section 8.10.6.

Subgroup	eGFR (mL/min)	CL (L/hr)	AUC 0-inf ( $\mu\text{M} \cdot \text{hr}$ )	Half-life (hr)
Normal	>90	4.18	50.9	4.47
Mild	60-89	3.17	67.1	5.89
Moderate	30-59	2.57	82.8	7.27
Severe	15-29	2.42	87.9	7.72
ESRD (not on dialysis)	<15	2.17	98.0	8.61
All parameter estimates are based on interim model results.				

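### Exploratory regression: the mild group is predicted at eGFR 60, described as its midpoint, but the midpoint of 60 to <90 is 75

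*Combined protocol and SAP*

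**What the plan says.** Section 9.6, Exploratory Regression Analysis, plans a regression in which untransformed AUC0-inf and Ceoi "will be evaluated with a linear fixed effects model containing eGFR as a continuous variable". Group means are then read off the fitted line, with each impairment group "predicted at the midpoint of the defined eGFR range for each group (60, 45, and 22.5 for mild, moderate, and severe, respectively"). The normal group is predicted at its observed median eGFR instead.

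The sample code has one ESTIMATE statement per group. The mild one is "estimate 'predicted AUC in mild' int 1 eGFR 60/alpha=0.1 cl e".

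If the straight line fits poorly, "natural log-transformed PK vs renal function or natural log-transformed PK vs natural log-transformed renal function, will be explored". Apart from the main run on BSA-normalized eGFR, "the analysis will also be run using BSA un-normalized eGFR and CrCL from CG equation".

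The group ranges are set in section 4.1, Table 6, and in inclusion criteria 8 to 10 (section 5.1): mild 60 to <90, moderate 30 to <60, severe 15 to <30 mL/min/1.73 m². The projection table in section 4.3 shows mild as 60-89.

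**The concern.** The plan gives a rule and three values, and one value breaks the rule. For mild, 60 is the lower limit of the range, which is also the upper limit of moderate. Because text and code agree, checking the program against the SAP would not catch the error.

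The consequence is a mislabelled result. Exposure rises as eGFR falls, so a mild prediction taken at 60 overstates mild exposure and makes mild and moderate look more alike than the fitted line says. Section 4.2 states that the study should inform dose adjustment in each impairment category, so a prediction carrying a category's name should represent that category.

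**Working it through.** **Midpoints, from the Table 6 ranges**

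| Group | Range | (lower + upper)/2 | Plan |
|---|---|---|---|
| Severe | 15 to <30 | 22.5 | 22.5 |
| Moderate | 30 to <60 | 45 | 45 |
| Mild | 60 to <90 | 75 | 60 |

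Other readings of midpoint do not give 60 for mild: whole-number bounds give (60+89)/2 = 74.5, and the geometric midpoint is √(60×90) = 73.5. The midpoint of 30 to 90 is 60, but no group has that range.

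**Gap between the mild and moderate predictions**

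With AUC = a + b × eGFR:
- intended: pred(45) − pred(75) = −30b
- as written: pred(45) − pred(60) = −15b
- ratio: 15/30 = 0.50, for any a and b.

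The ratio is also 0.50 on the log scale in the log-linear fallback. In the log-log fallback it is ln(60/45)/ln(75/45) = 0.288/0.511 = 0.56.

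**Rise in the mild AUC0-inf prediction (projection only)**

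Inputs are the section 4.3 projections of AUC0-inf in µM·hr: normal 50.9, mild 67.1, moderate 82.8, severe 87.9, ESRD 98.0. The table says "All parameter estimates are based on interim model results" but does not state the eGFR at which each value applies, so two placements were assumed.

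*Placement A, class midpoints* (mild 75, moderate 45, severe 22.5, ESRD 7.5). Worked example with normal at 100 and ESRD left out:
- least-squares slope −0.485, giving pred(75) = 65.2 and pred(60) = 72.5
- ratio 72.48/65.20 = 1.112.

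With normal at 95 to 120 and ESRD in or out, the ratio runs from 1.086 to 1.119.

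*Placement B, a clearance line.* Section 4.3 says "It is assumed that there is generally a linear relationship between eGFR and" renal clearance. The line CL = 1.97 + 0.02 × eGFR is not in the documents, but it reproduces the tabulated CL of 3.17, 2.57, 2.42 and 2.17 L/hr at eGFR 60, 30, 22.5 and 10. Straight-line AUC fits at those placements, with normal at 95 to 120 and ESRD in or out, give ratios of 1.084 to 1.134.

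*Direct check on that line, without a regression:* CL(60) = 3.17 and CL(75) = 1.97 + 1.50 = 3.47 L/hr. The AUC ratio is 3.47/3.17 = 1.095 (67.1 against 61.3).

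*Simple interpolation between 67.1 at eGFR 75 and 82.8 at 45:*
- slope 15.7/30 = 0.523 per unit of eGFR
- AUC at 60 = 67.1 + 15 × 0.523 = 74.95, a rise of 11.7%.

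*Wider settings* (placement A with normal at 90 to 125, 6 to 18 controls, ESRD out or at 5 to 10) give 8.0% to 14.1% for the straight line, 8.5% to 13.7% log-linear and 4.2% to 9.6% log-log.

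**The case against.** Four points can be made for leaving this alone.

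- **No mild-moderate contrast is planned.** The code gives four separate predicted means, and the formal comparisons are each group against controls, from a different model. That is true: the halving appears only when two outputs are compared. The mild prediction itself is still wrong.
- **The size depends on the model.** If clearance is linear in eGFR, AUC is curved, so the straight line may fail its lack-of-fit check. Under the log-log fallback the rise is smaller: 4.9% to 8.6% with the two placements above. This stands, so about 10% applies to the planned straight line. The 13.4% upper end is also weakly supported. It needs normal at 95 with ESRD included, whereas the clearance line puts the normal CL of 4.18 at eGFR 110.5, where the fits give 9.7% to 10.5%.
- **The right value is recoverable.** The slope and intercept are reported, and the plots carry confidence bands, so a careful reader could work out the prediction at 75. That limits the harm but does not correct the labelled output.
- **The 60 may be deliberate.** On the inferred clearance line the mild projection falls at 60. On the same line moderate falls at 30, yet the plan uses 45, so a lower-limit rule does not explain the three values either.

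Recurrence in the un-normalized eGFR and Cockcroft-Gault runs is conditional, because the plan gives no prediction points for them.

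**Conclusion.** The concern holds, and it is minor. The mismatch between 60 and 75 and the exact halving under the straight-line model rest only on the plan's own ranges and model. The rise of about 10% in the predicted mild AUC0-inf (8.4% to 13.4%) is a projection: it depends on the section 4.3 figures, on assumed eGFR placements and on the straight line being kept.

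The effect is confined to one exploratory prediction. The primary categorical ratios, the fitted slope and intercept, and the moderate, severe and normal predictions do not change. Ceoi should be little affected, since section 4.2 says that a change in Cmax "following a single dose is not anticipated".

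**What to change.** Replace 60 with 75 for the mild group in the section 9.6 text and in the mild ESTIMATE statement; keep 45 and 22.5. If the same prediction points are reused for the un-normalized eGFR and Cockcroft-Gault runs, carry the correction there too. The cost is one number in the text and one in the sample code. Data collection and the other analyses are untouched.
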